## 2. SYNOPSIS

|                  |  |
|------------------|--|
| Protocol Number  | DSXS-1303  |
| Title            | An Open Label, Safety Study to Assess the Potential for Adrenal Suppression and Pharmacokinetics Following Maximal Use Treatment with TOPICORT® (desoximetasone) Topical Spray, 0.25% in Pediatric Patients with Plaque Psoriasis  |
| Objectives       | The objective of this study is to evaluate the potential of TOPICORT® (desoximetasone) Topical Spray, 0.25% to suppress HPA axis function.

The secondary objectives are to evaluate the efficacy parameters, pharmacokinetics and adverse event (AE) profile.   |
| Sponsor          | TARO Pharmaceuticals USA, Inc.   |
| Test Product     | TOPICORT® (desoximetasone) Topical Spray, 0.25%  |
| Study Design     | 
An open label, post marketing safety study to assess the potential of a TOPICORT® (desoximetasone) Topical Spray, 0.25% to suppress HPA axis function following twice daily dosing for 28 days.
 
Up to one hundred (100) patients 2-17 years of age with a confirmed diagnosis of moderate to severe plaque psoriasis with involvement of <math>\geq 10\%</math> of their body surface area (excluding face and scalp). The participants will be serially enrolled into 3 cohorts.
 
Cohort 1: 12 years to 17 years and 11 months of age (up to 20-40 subjects)
 Cohort 2: 6 years to 11 years and 11 months of age (up to 20-30 subjects)
 Cohort 3: 2 years to 5 years and 11 months of age (up to 10-30 subjects)
 
Approximately 12 patients from each cohort will be included in a subgroup for PK profile determination. To minimize blood collection in young subjects in Cohorts 2 and 3 more sparse samplings may be done with lower age groups based on the PK profiles observed in Cohort 1. Prior to Cohort 2, all PK data from Cohort 1 will be analyzed and the protocol will be amended and submitted for IRB approval. The same procedure will be followed to analyze Cohort 2 data prior to Cohort 3.
 
If during the study more than 35% of dosed subjects from each cohort are considered to be exhibiting signs (confirmed by the results of a cortisol response test) and/or symptoms (nausea, headache, fatigue, myalgia or loose stool) of HPA axis suppression, the enrollment for this cohort will be stopped and the enrollment for a younger cohort(s) will not be initiated.
 
A patient will be considered to have potential HPA axis suppression if they meet at least one of the criteria:
 
 
• their 30 minute post injection cortisol level is not at least 7 mcg/100 ml greater than the basal level (<math>< \text{basal} + 7</math>)
 
• the post stimulation level is <math>\leq 18</math> mcg/100 ml
 
 
Two planned interim analyses will be conducted to evaluate safety following the end of the treatment periods for cohorts 1 and 2.
 |
| Study Population | Up to one hundred (100) patients 2-17 years of age with a confirmed diagnosis of plaque psoriasis with involvement of $\geq 10\%$ of their body surface area (excluding  |

|               |   |
|---------------|---|
|               | 
face and scalp) will be enrolled. The participants will be serially enrolled into 3 cohorts.
 
Cohort 1: 12 years to 17 years and 11 months of age (up to 20-40 subjects)
 Cohort 2: 6 years to 11 years and 11 months of age (up to 20-30 subjects)
 Cohort 3: 2 years to 5 years and 11 months of age (up to 10-30 subjects)
 
Enrollment for each cohort will be open for 6 months or less if the cohort is filled.
 
Approximately 12 patients from Cohort 1 will be included in a subgroup for PK profile determination. To minimize blood collection in young subjects in Cohorts 2 and 3 more sparse samplings may be done with lower age groups based on the PK profiles observed in Cohort 1. Prior to Cohort 2, all PK data from Cohort 1 will be analyzed and the protocol will be amended and submitted for IRB approval. The same procedure will be followed to analyze Cohort 2 data prior to Cohort 3.
 
If during the study more than 35% of dosed subjects from each cohort are considered to be exhibiting signs (confirmed by the results of a cortisol response test) and/or symptoms (nausea, headache, fatigue, myalgia or loose stool) of HPA axis suppression, the enrollment for this cohort will be stopped and the enrollment for a younger cohort(s) will not be initiated.
 
A patient will be considered to have potential HPA axis suppression if they meet at least one of the criteria:
 
 
• their 30 minute post injection cortisol level is not at least 7 mcg/100 ml greater than the basal level (< basal + 7)
 
• the post stimulation level is <math>\leq</math> 18 mcg/100 ml
 
 |
| Study Conduct | 
All patients will attend the clinic for 3 scheduled visits:
 
Visit 1: Baseline (Day 1)
 Visit 2: Day 15 <math>\pm</math> 2 (Interim visit)
 Visit 3: Day 29 <math>\pm</math> 2 (End of treatment or Early Termination)
 
Approximately 12 patients from Cohort 1 will be included in a subgroup for PK profile determination. The following visits will be scheduled for this subset of patients:
 
Cohort 1:
 
Visit 1: Baseline (Day 1)
 Visit 2: Day 8 <math>\pm</math> 2 (interim visit)
 Visit 3: Day 15 <math>\pm</math> 2 (interim visit)
 Visit 4: Day 22 <math>\pm</math> 2 (interim visit)
 Visit 5: Day 29 <math>\pm</math> 2 (End of treatment or Early Termination)
 Visit 6: Day 30 + 1 (Post Treatment Visit – Cortisol Response Test)
 
Morning pre-dose blood samples will be collected at Visits 1-5 with PK sampling at 15 min, 30 min, 40 min, 50 min, 60 min, 1.5 hr, 2 hr, 3 hr, 4 hr, 6 hr, 8 hr, 12 hr post-dose at Visit 5.
 
Cohort 2: Visit and blood sampling schedules will be included in the protocol amendment after completion of Cohort 1.
 
Cohort 3: Visit and blood sampling schedules will be included in the protocol amendment after completion of Cohort 2.
 
There will be 3 planned safety follow-up visits (Day 56, Day 84 and Day 112 after discontinuing treatment) for patients who exhibited signs of adrenal suppression
   |

|                    |  |
|--------------------|--|
|                    | during the study or at Visit 6 (Cohort 1).   |
| Inclusion Criteria | 
 
1. Male or female 2-17 years of age (inclusive) at Screening:
 Cohort 1: male or female 12 years to 17 years and 11 months of age
 Cohort 2: male or female 6 years to 11 years and 11 months of age
 Cohort 3: male or female 2 years to 5 years and 11 months of age
 
2. Signed IRB approved informed consent given by parent(s) or legally acceptable guardian(s) following their receipt of verbal and written information about the study.
 
3. Patients ages 7 years and older must have provided IRB approved written assent; this written assent must be accompanied by an IRB approved written informed consent from the Subject's legally acceptable representative (i.e., parent or guardian).
 
4. Female patients of childbearing potential (post-menarchal), in addition to having a negative urine pregnancy test, must be willing to use an acceptable form of birth control during the study from the day of the first dose administration to 30 days after the last administration of study drug. For the purpose of this study the following are considered acceptable methods of birth control: oral or injectable contraceptives, contraceptive patches, Depo-Provera® (stabilized for at least 3 months) NuvaRing® (vaginal contraceptive); Implanon™ (contraceptive implant) double barrier methods (e.g. condom and spermicide), IUD, or abstinence with a 2nd acceptable method of birth control should the Subject become sexually active. A sterile sexual partner is NOT considered an adequate form of birth control.
 
5. A definite clinical diagnosis of stable plaque psoriasis with involvement of <math>\geq 10\%</math> BSA (excluding face and scalp) 
 
If subject has both guttate and plaque psoriasis, majority of lesions must be plaque type and plaque type psoriasis must cover a minimum of 5% BSA.
 
 
 
6. Physicians Global Assessment (PGA) score of 3 (moderate) or 4 (severe) at baseline for the overall disease severity.
 
 |

|                         |  |
|-------------------------|--|
| Route of Administration | Topical  |
| Criteria for Evaluation | 
Primary Outcome Measures:
 
Hypothalamic Pituitary Adrenal (HPA) Axis Response to Cosyntropin demonstrating the absence or presence of adrenal suppression at the end of the treatment
 
Secondary Outcome Measures:
 
 
• Changes on the Physician Global Assessment (PGA) score at the end of treatment.
 
• Changes on the Clinical Signs and Symptoms (erythema, scaling, plaque elevation) at the end of treatment.
 
• Pharmacokinetic parameters for desoximetasone at the end of treatment.
 
   |
| Statistical Analysis    | 
Primary analysis:
 
 
• Proportion of patients in the study with HPA axis suppression following treatment with the study medication.
 
 
Secondary analyses:
 
 
• Proportion of patients in each cohort with HPA axis suppression following treatment with the study medication.
 
• The frequency, severity, and relationship to study drug for AEs will be used to evaluate the safety profile of the study drug.
 
• A descriptive analysis on changes in PGA and Clinical Signs and Symptoms.
 
 
Two planned interim analysis will be conducted following the end of the treatment periods for cohorts 1 and 2.
 |

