### 6.2 Statistical Analyses

Patients are required to apply a total of 56 doses for the study. Patients will dose twice daily for 28 days. Patients in the PK Sampling Group will dose in the office at End of Treatment Visit. All patients who are enrolled and used at least 75%-125% of scheduled doses (i.e., between 42 - 70 doses) of the study drug and have data from a post-treatment cortisol response test will be included in the analysis.

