***TOPICORT® (desoximetasone) Topical Spray, 0.25% Pediatric HPA Axis study***

---

The test at the End of Study visit should not be performed if the patient dosed within 8 hours.

HPA axis suppression will be defined as a 30 minute post-CortrosynTM injection level cortisol level of  $\leq$  18 mcg/100 mL.

Any patient with abnormal test results, as defined above, will be considered to be exhibiting signs of HPA axis suppression. As the study treatment period will be over, any patients with abnormal results will be advised not to initiate any new steroid therapy, topical or otherwise, and to return to the site in 28 days at which time they will be assessed for HPA axis suppression.

Any patient presenting with symptoms of HPA axis suppression, such as nausea, headache, myalgia, fatigue or loose stool, will be referred to an endocrinologist. As an additional safety precaution, wristbands identifying the patient as someone suffering from adrenal suppression secondary to steroid withdrawal will be provided to alert medical personnel should any emergencies arise before adrenal function returns to normal.

If the results of the cortisol response test still show signs of HPA axis suppression 28 days after discontinuing therapy they will be asked to return in 28 days (56 days after discontinuing steroid therapy) for another follow-up test. If the patient is still showing signs of HPA axis suppression 56 days after discontinuing steroid therapy and presents with related symptoms they will be referred to an endocrinologist.

If HPA axis suppression persists for 56 days after discontinuing steroid therapy, but the patient has no symptoms they will be asked to return in 28 days (84 days after discontinuing steroid therapy) for another follow-up test. If HPA axis suppression persists for 84 days after discontinuing steroid therapy patients will be referred to an endocrinologist regardless of symptoms.

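### Retests for children with suppressed adrenal function are set at 56, 84 and 112 days off treatment in the synopsis but at 28, 56 and 84 days in the SAP, so the synopsis as written has no 28-day retest

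*Combined protocol and SAP*

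**What the plan says.** The synopsis, under Study Conduct, covers children who showed signs of adrenal suppression during the study or at Visit 6 (Cohort 1): "There will be 3 planned safety follow-up visits (Day 56, Day 84 and Day 112 after discontinuing treatment".

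SAP section 6.2.1 describes a stepwise sequence. A child with an abnormal end-of-study result is told "to return to the site in 28 days at which time they will be assessed for HPA axis suppression". The next sentence on retesting gives the time origin: "If the results of the cortisol response test still show signs of HPA axis suppression 28 days after discontinuing therapy". Children still suppressed at that point are asked to "return in 28 days (56 days after discontinuing steroid therapy) for another follow-up test". At that second test, a child who is still suppressed "56 days after discontinuing steroid therapy and presents with related symptoms they will be referred to an endocrinologist", while one without symptoms comes back at 84 days. The sequence ends there: "If HPA axis suppression persists for 84 days after discontinuing steroid therapy patients will be referred to an endocrinologist regardless of symptoms".

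Two other statements bear on when treatment stops. The synopsis labels its last treatment visit, Day 29 ± 2, as "End of treatment or Early Termination", so early stopping is provided for. SAP section 6.2 adds: "Patients in the PK Sampling Group will dose in the office at End of Treatment Visit".

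**The concern.** Both texts measure from discontinuation, yet they list different days. Only 56 and 84 appear in both.

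The 28-day test matters because the rest of the SAP sequence depends on it: the 56-day test is done only if suppression persists at 28 days, and the 84-day test only if it persists without symptoms at 56 days. A site working from the synopsis alone would first retest a suppressed child 56 days after stopping. Until then no scheduled test would show either recovery or persistence, and the child would remain under the SAP's advice not to start new steroid treatment. The synopsis also lists a visit at 112 days, for which the SAP plans no test because persistence at 84 days already leads to referral.

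Adrenal suppression is the trial's primary safety question, in children as young as 2 years. The schedule for following an affected child should therefore read the same way in both places.

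**Working it through.** **Inputs**

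- Synopsis, Study Conduct: 56, 84 and 112 days after discontinuing.
- SAP 6.2.1: 28, 56 and 84 days after discontinuing.
- SAP 6.2: twice-daily dosing for 28 days, so a completing patient's last dose falls on Day 28. In the PK group it falls at the End of Treatment Visit, taken here as Day 29.
- SAP 6.2.1, Descriptive Summary: post-treatment cortisol test at Day 30.

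**Direct comparison.** The days common to both are 56 and 84. Day 28 is in the SAP only and Day 112 in the synopsis only.

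**Literal reading.** Study day = last-dose day + days off drug. For a last dose on Day 28:

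| Schedule | Days off drug | Study days |
|---|---|---|
| SAP | 28, 56, 84 | 28+28 = 56, 28+56 = 84, 28+84 = 112 |
| Synopsis, literal | 56, 84, 112 | 28+56 = 84, 28+84 = 112, 28+112 = 140 |

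From a Day 30 test to the first retest is 56 − 30 = 26 days under the SAP and 84 − 30 = 54 days under the literal synopsis. If the test is on Day 29, the gaps are 27 and 55 days. The difference is 28 days in both cases.

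**Study-day reading.** Suppose the synopsis figures are study days. Days off drug are then 56 − L, 84 − L and 112 − L for a last dose on Day L, and the lag behind the SAP is 28 − L at every visit.

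| Last dose (Day L) | Days off drug | Lag behind the SAP |
|---|---|---|
| 28 | 28, 56, 84 | 0 |
| 29 (PK group) | 27, 55, 83 | −1 (one day early) |
| 21 (assumed) | 35, 63, 91 | 7 |
| 14 (assumed) | 42, 70, 98 | 14 |
| 7 (assumed) | 49, 77, 105 | 21 |

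The documents give no last-dose days for early terminations, so the last three rows are illustrative. The study-day reading reproduces the SAP exactly only for a last dose on Day 28.

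**The case against.** The strongest reply is that this is a labelling slip and that no retest was dropped. Both texts plan three tests 28 days apart, and the offset between them equals the treatment period. Read as study days, the synopsis agrees with the SAP for a patient who finishes on Day 28. As an account of how the error arose, this is probably right. It does not rescue the text, which gives the days as counted from discontinuation, and the study-day reading still fails for early terminations.

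The two documents may also come from different stages of the protocol. The SAP already contains Cohort 2 sampling times that the synopsis leaves to an amendment, and it calls Day 29 Visit 6 where the synopsis calls it Visit 5. The full visit schedule is not in the text supplied, so the instructions sites actually followed are unknown. That limits any claim about what happened to patients, but the two statements still disagree.

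The safety effect is also limited. The SAP's referral points at 56 and 84 days have a visit under both schedules. Children with symptoms are referred with no visit day attached. A 112-day visit after an 84-day referral is superfluous under the SAP but contradicts nothing. No primary or secondary analysis uses these visits. All of this stands.

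On the arithmetic, three cautions are fair:

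- The 26- and 54-day gaps combine a Day 28 last dose with a Day 30 test, although the synopsis lists a Day 30 visit only for the PK subgroup. Only the 28-day difference is firm.
- The one-day discrepancy for the PK group is trivial beside the ± 2-day visit window.
- The 28-day delay belongs to the literal reading and the early-termination lags to the study-day reading, so the two are alternatives and must not be added.

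Finally, the SAP's first instruction could be read as 28 days from the abnormal result, but its following text fixes the count at discontinuation.

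**Conclusion.** The inconsistency is real and should be corrected. Taken at its word, the synopsis leaves out the 28-day retest and puts the first retest 28 days later than the SAP does. Taken as study days, it matches the SAP for a last dose on Day 28. It would then be 7 to 21 days late for early terminations with assumed last doses between Day 21 and Day 7. Under either reading the anchor has to be stated correctly.

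The consequence is confined to the follow-up of children with an abnormal cortisol test. The estimated proportion with suppression and the other planned analyses are unaffected. The conflict itself is read directly from the two texts and needs no assumption. The conversions to study days assume a last dose on Day 28 unless another day is shown.

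**What to change.** Reword the synopsis to place the three retests at 28, 56 and 84 days after the last dose, adding that these are study Days 56, 84 and 112 for patients who complete 28 days of treatment. Counting from the last dose makes the schedule hold for early terminations and for the PK group's Day 29 dose. A visit window would be useful but is optional.

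If the sponsor's clinicians confirm that 56, 84 and 112 days off treatment was intended, SAP section 6.2.1 should be changed instead, including its 28-day first step and its referral points.

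The synopsis correction is one line. It adds no visits to the SAP's schedule and changes no planned analysis. It can go into one of the protocol amendments already planned before the younger cohorts open.

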## STATISTICAL ANALYSIS PLAN

IND # 101789/ NDA # 204141

Protocol No. DSXS-1303

***TOPICORT® (desoximetasone) Topical Spray, 0.25% Pediatric HPA Axis study***

---

### 6. STATISTICAL ANALYSIS METHODS

If not otherwise specified, statistical significance is defined as  $p < 0.05$  and is two-tailed. Data will be summarized with respect to demographic and baseline characteristics, efficacy variables and safety variables.

For categorical variables, the number and percent of each category within a parameter will be calculated for non-missing data. For continuous variables, statistics will include number of observations, mean, standard deviation, median, minimum and maximum values.

All statistical analyses will be conducted using SAS®, Version 9.4 or higher. Datasets will be prepared using headings from Clinical Data Interchange Consortium (CDISC) Study Data Tabulation Model (SDTM) implementation for human clinical trials and ADaM (Analysis Dataset Model).

## STATISTICAL ANALYSIS PLAN

IND # 101789/ NDA # 204141

Protocol No. DSXS-1303

***TOPICORT® (desoximetasone) Topical Spray, 0.25% Pediatric HPA Axis study***

---

### 6.1 Baseline Characteristics

#### 6.1.1 Demographics

Demographic information collected at baseline includes the following:

- Age (years)
- Gender (Male/Female)
- Ethnicity (Hispanic/non Hispanic)
- Race (White, Black/African American, Native Hawaiian or Other Pacific Islander, Asian, American Indian or Alaska Native, Other)
- Weight
- Height

Summary tables by cohort and by PK subgroup within a cohort will be presented. Continuous variables will be summarized using descriptive statistics (n, median, minimum, maximum, mean, standard deviation). Categorical variables will be summarized using frequencies and percentages.

Baseline comparability of the treatments will be presented using Cochran-Mantel-Haenszel (CMH) test for the categorical variables, and Analysis of Variance for the continuous variables.

All data will be listed by cohort, PK subgroup within a cohort, and patient.

### 6.2 Statistical Analyses

Patients are required to apply a total of 56 doses for the study. Patients will dose twice daily for 28 days. Patients in the PK Sampling Group will dose in the office at End of Treatment Visit. All patients who are enrolled and used at least 75%-125% of scheduled doses (i.e., between 42 - 70 doses) of the study drug and have data from a post-treatment cortisol response test will be included in the analysis.

#### 6.2.1 Primary Analysis

##### **Potential HPA axis suppression**

The following criteria indicate a normal cortisol response (all criteria must be met):

1. Their basal (pre-Cortrosyn™ injection) cortisol concentration is > 5 mcg/100 mL
2. Their 30 minute post injection cortisol level is at least 7 mcg/100 mL greater than the basal level ( $\geq$  basal value + 7)
3. The post stimulation level is > 18 mcg/100 mL

Patients found to have abnormal adrenal function after the baseline Cortisol Response Test will not be enrolled in the study.

## STATISTICAL ANALYSIS PLAN

IND # 101789/ NDA # 204141

Protocol No. DSXS-1303

***TOPICORT® (desoximetasone) Topical Spray, 0.25% Pediatric HPA Axis study***

---

The test at the End of Study visit should not be performed if the patient dosed within 8 hours.

HPA axis suppression will be defined as a 30 minute post-CortrosynTM injection level cortisol level of  $\leq$  18 mcg/100 mL.

Any patient with abnormal test results, as defined above, will be considered to be exhibiting signs of HPA axis suppression. As the study treatment period will be over, any patients with abnormal results will be advised not to initiate any new steroid therapy, topical or otherwise, and to return to the site in 28 days at which time they will be assessed for HPA axis suppression.

Any patient presenting with symptoms of HPA axis suppression, such as nausea, headache, myalgia, fatigue or loose stool, will be referred to an endocrinologist. As an additional safety precaution, wristbands identifying the patient as someone suffering from adrenal suppression secondary to steroid withdrawal will be provided to alert medical personnel should any emergencies arise before adrenal function returns to normal.

If the results of the cortisol response test still show signs of HPA axis suppression 28 days after discontinuing therapy they will be asked to return in 28 days (56 days after discontinuing steroid therapy) for another follow-up test. If the patient is still showing signs of HPA axis suppression 56 days after discontinuing steroid therapy and presents with related symptoms they will be referred to an endocrinologist.

If HPA axis suppression persists for 56 days after discontinuing steroid therapy, but the patient has no symptoms they will be asked to return in 28 days (84 days after discontinuing steroid therapy) for another follow-up test. If HPA axis suppression persists for 84 days after discontinuing steroid therapy patients will be referred to an endocrinologist regardless of symptoms.

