### **Descriptive Summary**

The primary analysis will be proportion of evaluable patients across all age cohorts with HPA axis suppression, as observed from results of a cortisol response (ACTH stimulation) test at Day 30 (Post Treatment). Evaluable subjects are those that have both a baseline and end-of-study Cortisol Response Test results and have not been identified as having enrolled in the study previously. Patients found to have abnormal adrenal function after the baseline Cortisol Response Test will not be included in the evaluable patients for analysis.

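### The end-of-study cortisol test has a minimum gap from the last dose but no stated maximum, so recovery after early stopping can lower the primary suppression proportion

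*Combined protocol and SAP*

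**What the plan says.** - **Timing relative to dosing.** SAP 6.2.1 states: "The test at the End of Study visit should not be performed if the patient dosed within 8 hours". This is a lower limit only. The supplied text has no upper one.
- **Timing by calendar.** The Descriptive Summary under SAP 6.2.1 takes the primary result "as observed from results of a cortisol response (ACTH stimulation) test at Day 30 (Post Treatment"). In the Synopsis (Study Conduct), a post-treatment cortisol visit on Day 30, or up to one day later, is listed for the Cohort 1 PK subgroup. The other schedule ends with a visit on Day 29 ± 2, which also serves as the early-termination visit. No interval from the last dose is attached to any of these.
- **First inclusion rule, SAP 6.2.** "Patients are required to apply a total of 56 doses for the study", and the analysis takes patients who "used at least 75%-125% of scheduled doses (i.e., between 42 - 70 doses) of the study drug" and have a post-treatment cortisol test.
- **Second inclusion rule, Descriptive Summary under SAP 6.2.1.** "Evaluable subjects are those that have both a baseline and end-of-study Cortisol Response Test results". It also requires no previous enrolment and a normal baseline test. It has no dose count and no condition on the last dose.
- **Outcome.** The Synopsis (Criteria for Evaluation) defines the primary outcome as presence or absence of adrenal suppression when treatment ends.
- **Reversibility.** SAP 6.2.1 schedules retests after stopping and provides wristbands "should any emergencies arise before adrenal function returns to normal".

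**The concern.** A normal cortisol response soon after the last dose is evidence that treatment did not suppress the axis. A normal response a week or more after the last dose could mean that, or that suppression occurred and resolved. The plan counts both as not suppressed.

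The plan itself expects function to return after treatment stops, so the two situations are not interchangeable. The error has one direction: recovery before the test removes cases from the numerator and leaves the denominator unchanged. In a maximal-use safety study, that is the direction that makes the product look safer. The affected children are those who stop dosing early, and some may do so because of symptoms.

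**Working it through.** **1. The plan's own figure.** Two doses a day for 28 days is 2 × 28 = 56 doses. Then 0.75 × 56 = 42 and 1.25 × 56 = 70. The stated range of 42 to 70 is reproduced.

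**2. Gap from last dose to test.** Assume twice-daily dosing from Day 1, an evening last dose and a morning test. Gap in days = test day − last-dose day − 0.5.

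| Dosing pattern | Last dose | Test Day 29 | Day 30 | Day 31 |
|---|---|---|---|---|
| All 56 doses | Day 28 | 0.5 | 1.5 | 2.5 |
| 42 consecutive doses (42 / 2 = 21 days) | Day 21 | 7.5 | 8.5 | 9.5 |

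At the early edge of the Day 29 ± 2 window (Day 27), the 42-dose child is 5.5 days off drug. Both rows satisfy both inclusion rules, so two children in one analysis set can differ by 7 days off drug.

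**3. Effect on the primary proportion.** Let p be the true rate when dosing ends, f the share of children tested late (with the same true rate as the rest), and r the share of the suppressed among them who have recovered by the test. Reported rate = p × (1 − f × r). The documents give none of p, f or r, so all three are assumptions. For p = 20%:

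| f | r = 25% | r = 50% | r = 100% |
|---|---|---|---|
| 5% | 19.8% | 19.5% | 19.0% |
| 10% | 19.5% | 19.0% | 18.0% |
| 20% | 19.0% | 18.0% | 16.0% |

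For p = 35% the same ranges give 34.6% down to 28.0%.

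**4. How a limit behaves.** Take 100 children, a true rate of 20%, and 20 tested late, of whom 20 × 0.20 = 4 were suppressed. The other 80 contribute 16 cases.

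- All tests kept: (16 + 4(1 − r)) / 100. At r = 0.5 this is 18/100 = 18.0%.
- All late tests excluded: 16/80 = 20.0% for any r.
- Only late normal results excluded: (16 + 4(1 − r)) / (80 + 4(1 − r)). At r = 0.5 this is 18/82 = 22.0%; at r = 0.25, 19/83 = 22.9%; at r = 0, 20/84 = 23.8%.

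A limit that removes only normal results therefore selects on the outcome. Below about r = 0.5 its error is larger than that of the present rule.

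**The case against.** **The dose count already limits the gap.** It does so indirectly. A reader might infer that a child who stops on Day 10 and is tested on Day 29, about 19 days off drug, is evaluable. Such a child has about 20 doses and fails the 42-dose rule in SAP 6.2, the parent section of 6.2.1. The longer gap appears only if the evaluable definition is read without that rule. With the rule applied, the gap at twice-daily dosing is at most about 9.5 days on Day 31. The two definitions still differ and need to be reconciled.

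**Early stoppers have a termination visit.** The Synopsis foresees one, so not every early stopper waits until Day 29 or later. The visit has no stated interval from the last dose, however, and it does not catch a child who stops applying the spray but keeps attending on schedule.

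**Low dose counts need not mean early stopping.** This stands. A child with 42 scattered doses may be tested soon after the last one. Only early stopping or late non-adherence creates the gap.

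**Recovery within 8 to 10 days is not documented.** This also stands. The retests at 28, 56 and 84 days allow for suppression that persists. They show that recovery is expected, not how fast it occurs.

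**The shift is small beside sampling error.** At 20% with the maximum of 100 children, the 95% half-width is 1.96 × √(0.2 × 0.8 / 100), about 8 points, against an illustrative shift of at most 4 points. That limits the practical weight, but the interval does not correct a one-directional bias.

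**A limit may sit elsewhere.** Only the Synopsis and SAP section 6 are available, so this cannot be excluded. The evaluable definition would still need a cross-reference to it.

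**Conclusion.** The point holds in limited form. In the supplied text nothing bounds the time from last dose to test from above. A child who satisfies both inclusion rules can be about 7.5 to 9.5 days off drug at a Day 29 to 31 test, and a normal result then counts as not suppressed. Any resulting bias is towards less suppression.

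Its size cannot be derived from the documents. The range of 19.8% down to 16.0% for a true 20% rests wholly on the assumed f of 5-20% and r of 25-100%. With no recovery before the test there is no bias.

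A reader might infer two further things that the documents do not establish. One is that the reported rate will be materially wrong, which would need a recovery time and an early-stop rate. The other is that the 35% rule for stopping cohort enrolment is undermined. That rule counts dosed subjects, and symptoms as well as test results, so it is not tied to the evaluable set. Nothing in the text shows that a late normal test would change it.

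**What to change.** In SAP 6.2.1:

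- Derive hours from last dose to end-of-study test and list them by patient. The last-dose time is already needed to apply the 8-hour rule.
- Pre-specify a maximum interval, with the sponsor's justification. It should cover a fully adherent child tested within the visit window: evening of Day 28 to morning of Day 31 is about 2.5 × 24 = 60 hours. A limit of 48 hours, for example, would drop such children.
- Apply the limit to normal and abnormal results alike.
- Report the primary proportion twice: with all tested children, and with all tests beyond the limit excluded. The second figure could itself be too low if early stoppers have a higher true rate, so neither should stand alone.
- Show late abnormal results on a separate line so that no suppression case is hidden.
- Reconcile the dose-count rule in SAP 6.2 with the evaluable definition in 6.2.1, and reconcile the Day 30 test there with the Synopsis schedules.

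The cost is SAP wording, one derived variable and one extra analysis. The denominator is slightly smaller in one of the two analyses, and the rate may be less favourable.
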